- To explore the following efficacy endpoints in subjects with moderately to severely active UC

subjects with moderately to severely active UC who do not achieve clinical response after 12 weeks of induction therapy in the study stage 1, thereby to evaluate the efficacy of CBP-307 when orally administered for treatment in the sub-study 2 of the study stage 2.

who achieved clinical response after 12 weeks of induction therapy in study stage 1:

- Percentage of subjects who maintain clinical response at week 48
- o Percentage of subjects who achieve clinical remission at week 48
- Percentage of subjects who achieve mucosal healing under endoscope at week 48
- Percentage of subjects who take oral corticosteroids at baseline but has discontinued treatment of corticosteroids at week 48 and achieved clinical remission
- O Change in the complete Mayo score at week 48 from baseline
- Change in the adapted Mayo score at week 48 from baseline
- To explore the following efficacy endpoints in subjects with moderately to severely active UC who do not achieve response after 12 weeks of induction therapy in study stage 1:
 - Percentage of subjects who achieve clinical response at week 24 (after 12 weeks of treatment in sub-study 2)
 - O Percentage of subjects who achieve clinical remission at week 24 (after 12 weeks of treatment in sub-study 2)
 - Percentage of subjects who achieve mucosal healing under endoscope at week 24 (after 12 weeks of treatment in sub-study 2)
 - O Change in the complete Mayo score at week 24 (after 12 weeks of treatment in sub-study 2) from week 12
 - O Change in the adapted Mayo score at week 24 (after 12 weeks of treatment in sub-study 2) from week 12
 - Percentage of subjects who maintain clinical response at week 48 (after 36 weeks of treatment in sub-study 2) (i.e., have clinical response at both week 24 and week 48)
 - O Percentage of subjects who achieve clinical remission at week 48 (after 36 weeks of treatment in sub-study 2)
 - Percentage of subjects who achieve mucosal healing under endoscope at week 48 (after 36 weeks of treatment in sub-study 2)
 - O Change in the complete Mayo score at week 48 (after 36 weeks of treatment in sub-study 2) from week 12

Protocol No.: CBP-307CN002 Confidential

0	Change in the adapted Mayo score at
	week 48 (after 36 weeks of treatment in
	sub-study 2) from week 12

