Sub-study 1 (subjects who have achieved clinical response by adapted Mayo score): Subjects who **have achieved clinical response** shown by efficacy evaluation at week 12 in the study stage 1 and meet the eligibility criteria for stage 2 will enter sub-study 1 of the study stage 2 to receive double-blind maintenance treatment for 36 weeks (weeks 13 to 48), i.e., the therapeutic regimen for them in study stage 1 will be continually maintained (Figure 2). Safety follow-up will be completed at 4 weeks after the last dose. Subjects who present with recurrent UC during maintenance treatment are required to terminate treatment and withdraw from the study.

For the subjects already enrolled as per the previous approved protocols (version 5.0 or earlier), they will follow the previous planned treatment in the sub-study 1 of stage 2 study.

UC disease recurrence i.e., an increased activity of UC, is defined as a repeated (occurring at 2 consecutive visits) partial Mayo score that is at least 5 points and is also ≥3 points higher than the score at week 12 (the end of induction therapy), and where the possibility of increased disease activity being due to other potential factors unrelated to UC can be excluded (e.g., infection, medication changes).

Sub-study 2 (subjects who have not achieved clinical response by adapted Mayo score): Subjects who **have not achieved clinical response** shown by efficacy evaluation at week 12 in the study stage 1 and meet the eligibility criteria for study stage 2 will enter open-label treatment with CBP-307 0.2 mg (Figure 2). Subjects will receive CBP-307 once daily at an oral dose of 0.2 mg in sub-study 2 regardless of whether they receive CBP-307 0.2 mg or placebo in the study stage 1.

For subjects who enter sub-study 2 of study stage 2, 1-week dose titration will be performed at the first week (week 13). Dose titration will involve administration of CBP 0.05 mg initiated on day 1 and used for 4 consecutive days, followed by administration of CBP-307 0.1 mg for 3 days, and administration of CBP-307 at a target dose of 0.2 mg initiated on day 8. After dose titration is completed, subjects will receive oral treatment with CBP-307 0.2 mg once daily, for 36 weeks. Safety follow-up will be completed at 4 weeks after the last dose.

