At week 24, subjects will undergo efficacy evaluation including colonoscopy. If any subject still has not achieved clinical response, the treatment will be discontinued and the subject will be withdrawn from the study.

Study stage 2 (Optional): Responders Study stage 1: 12-week, randomized, double-blind induction study enter the double-blind maintenance phase, and non-responders enter the 36 weeks open-label study Yes Placebo N=52 Substudy 1 Randomization and (1:1)N = 104CBP-30 Yes 0.2ms CBP-307 0.2m CBP-307 0.2mg Substudy 2 Open label

Figure 2 Schematic Diagram of Transition from Stage 1 to Stage 2 Substudies

Inclusion and exclusion criteria:

The following criteria are used to select eligible subjects for this study. A subject is eligible to be included in the study only if all of the inclusion criteria apply and none of the exclusion criteria apply.

Inclusion criteria:

Subjects are eligible to be included in the study only if all of the following criteria apply:

- 1. Male or female subjects aged 18-75 years (inclusive).
- 2. In the opinion of the investigator, the subject is capable of understanding and complying with protocol requirements. The subject signs and dates a written informed consent form prior to the initiation of any study procedures.
- 3. Female subjects of childbearing potential and male subjects who have not undergone vasectomy should use at least one **highly** effective method of contraception during the entire study and 4 weeks after the last dose of investigational products after signing the informed consent form. **The highly effective methods of contraception in this study include:**
 - a. Abstinence is acceptable only if it is part of the participant's regularly practiced lifestyle;
 - b. Hormone (oral, patch, ring, injection, implant) in combination with a male condom. This must be used for at least 30 days before the first dose of investigational products or an alternative acceptable method must be used;
 - c. Intrauterine device (IUD) in combination with a male condom;

- d. Exceptions are: a) women with at least 12 consecutive months amenorrhea in the absence of medications known to induce amenorrhea and have a documented follicle stimulating hormone (FSH) level of greater than 40 mIU/mL or in the postmenopausal range; or b) surgical sterilization (e.g., hysterectomy, bilateral oophorectomy).

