Study stage 2: All subjects who complete the 12-week study stage 1 treatment (induction therapy with CBP-307 or placebo) and complete all assessments (including colonoscopy) at week 12 visit can choose to enter the study stage 2 for a total of 40 weeks. In the stage 2, subjects will continuously be administered for 36 weeks (week 13-48 of the study), and they will undergo safety follow-up for 4 weeks after the last dose (week 49-52 of the study). Subjects who early withdraw from the study will undergo safety follow-up for 4 weeks after the last dose.

For subjects who complete both stages (stage 1 + stage 2), the study will last for a total of 52 weeks: 48 weeks of administration, and 4 weeks of follow-up.

Study procedures:

The study procedures in the stage 1 are shown in Table 2 Study Flow Chart.

Study procedures in the stage 2 are shown in Table 3 Study Flow Chart (sub-study 1) and Table 4 (sub-study 2).

Sample size:

Approximately 134 subjects with moderate to severe UC will be randomized in the study. Among them, approximately 30 subjects who have already enrolled in CBP-307 0.1 mg group based on protocol version 5.0 or earlier will be analyzed for exploratory purpose. No further subjects will be enrolled in CBP-307 0.1 mg group from protocol version 6.0.

Approximately 104 eligible subjects will be randomized at 1:1 into one of the following 2 groups to undergo induction therapy in the study stage 1: CBP-307 0.2 mg once daily, or placebo (52 subjects in each group) based on protocol amendment and sample size recalculation.

All subjects who complete the 12-week study stage 1 and all tests (including colonoscopy) at visit at week 12 can be selected to enter the study stage 2.

Statistical method:

The primary efficacy endpoint of the study is the change in adapted Mayo score from baseline at week 12 after treatment compared between CBP-307 0.2 mg and placebo at the study stage

1.

The sample size was calculated based on the estimation on primary efficacy endpoint. Assuming that the difference between the 0.2 mg group and the placebo group of the change from baseline at week 12 after treatment in adapted Mayo score is 1.2, and the common standard deviation is 2.0, a significance level of α =0.05 (two-sided), and a dropout rate is 15%, then each group needs to enroll at least 52 subjects to provide a power of 80% to detect the difference between the 0.2 mg group and the placebo group on the primary efficacy endpoint.

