- 1. Subjects who have completed the 12-week induction therapy of study stage 1 and have completed the evaluation of study visit 11 (see Table 1) while not achieved clinical response at visit 11, can choose the sub-study 2 of study stage 2 to receive open-label treatment of 0.2 mg CBP-307 daily. If the subject is eligible, the study process will follow this flow chart. Visit 12 is the screening visit in study stage 2, and the qualification assessment will be based on the results of visit 11. Subjects who meet the eligibility criteria for stage 2 and have not achieved clinical response will be enrolled in sub-study 2 of stage 2 and treated with 0.2mg CBP-307. The interval between the first administration of sub-study 2 and the last administration of study stage 1 will be less than 1 week.
- 2. Subjects eligible for inclusion in sub-study 2 of study stage 2 at visit 12 will receive dose titration for one week from visit 13. If the assessment at visit 12 meets the requirements and time permits, the dose titration can be started and the required procedures of visit 13 can be completed on the same day. The dose titration includes 0.05 mg CBP-307 for four consecutive days from the first day, 0.1 mg CBP-307 for the subsequent three days, and target dose of 0.2 mg CBP-307 will be started on the 8th day. Upon completion of the dose titration, subjects will receive oral treatment of 0.2 mg CBP-307 once a day.
- 3. Subjects are recommended to be followed up in the morning. At the indicated visits, subjects will be given medication at the site. If time permits, subjects in the study should be evaluated at roughly the same time. For subjects who cannot continue to participate in the study for any reason, the investigator should make every effort to complete the evaluation during the end of the study/early termination visit.
- 4. The signing of informed consent can also be done at visit 11 (week 12).

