Treatment Group	Target Visit Day	Mappe d Visit Day	Planned Daily Dose (mg)	Target Duration	Target Dose Level in the Target Visit (mg)	Planned Cumulative Dose (mg)
0.2 mg QD	W13D5	5	0.05	4	0.2	0.2
	W14D8	8	0.1	3	0.3	0.5
	W16D112	28	0.2	21	4.2	4.7
	W24D168	84	0.2	56	11.2	15.9
	W32D224	140	0.2	56	11.2	27.1
	W40D280	196	0.2	56	11.2	38.3
	W48D336	252	0.2	56	11.2	49.5

- Actual cumulative dose (mg) during the regular treatment period:

Actual cumulative dose (mg) is defined as the sum of the total dosage that the subject taken during the regular treatment period.

- Planned dose Intensity (mg/day) during the regular treatment period:

Planned dose intensity (mg/day) during the regular treatment period = planned cumulative dose (mg) during the regular treatment period/duration of exposure (days) during regular treatment period*100.

- Dose intensity (mg/day) during the regular treatment period:

Dose intensity (mg/day) during the regular treatment period = actual cumulative dose (mg) during the regular treatment period/duration of exposure (days) during regular treatment*100.

- Relative dose intensity (mg/day) during the regular treatment period:

Relative dose intensity (mg/day) during the regular treatment period=dose intensity during the regular treatment period/planned dose intensity during the regular treatment period*100.

Duration of exposure during the regular treatment period, total duration of exposure, planned cumulative dose during the regular treatment period, planned cumulative dose, actual cumulative

Document: Statistical Analysis Plan

Author: [name]

Version Number: 1.1

Version Date: 18Jan2023

Template No.: CS_TP_BS016 Revision 5

Reference: CS_WI_BS005

Effective Date: 01Apr2018

dose during the regular treatment period, total actual cumulative dose, planned dose intensity during the regular treatment period, dose intensity during the regular treatment period, relative dose intensity (mg/day) during the regular treatment period will be summarized using descriptive statistics, i.e., number of subjects (n), mean, median, standard deviation (SD), 25th and 75th percentiles (Q1, Q3), minimum and maximum.

In addition, the exposure data for the SS will be included in a listing.

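### Sub-study 2 visit days, endpoint labels and the SAP exposure table run on different clocks: for on-schedule subjects week 24 falls after 79 to 84 open-label doses, not a fixed 12 weeks

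*Protocol*

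**What the plan says.** **Endpoints.** The Protocol synopsis lists "Percentage of subjects who achieve clinical response at week 24 (after 12 weeks of treatment in sub-study 2" among the exploratory endpoints, with remission, mucosal healing and Mayo score changes on the same footing. The week-48 counterparts are described as 36 weeks of sub-study treatment. Protocol Sections 4 and 9.8.1 and SAP Section 14.4.1 repeat both labels.

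**Visit schedule.** Protocol Table 4 puts the stage 2 screening visit (visit 12) at Day 90 ±5. Note 2 says "Subjects eligible for inclusion in sub-study 2 of study stage 2 at visit 12 will receive dose titration for one week from visit 13", and that, if the subject qualifies at visit 12 and time permits, "the dose titration can be started and the required procedures of visit 13 can be completed on the same day". Note 1 adds: "The interval between the first administration of sub-study 2 and the last administration of study stage 1 will be less than 1 week". Titration Day 1 has no study day of its own. The week 16, 24, 32, 40 and 48 visits stay on the stage 1 count, at Days 112, 168, 224, 280 and 336 (each ±5).

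**Week-24 rule.** After the week-24 colonoscopy, "If any subject still has not achieved clinical response, the treatment will be discontinued and the subject will be withdrawn from the study".

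**SAP exposure table.** The sub-study 2 table in SAP Section 12 converts Day 112 to treatment day 28, Day 168 to day 84 and Day 336 to day 252. Its planned cumulative doses are 4.7, 15.9 and 49.5 mg.

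**Treatment length.** On duration, the synopsis says "In the stage 2, subjects will continuously be administered for 36 weeks (week 13-48 of the study". Its sub-study 2 description says "After dose titration is completed, subjects will receive oral treatment with CBP-307 0.2 mg once daily, for 36 weeks", and Protocol Section 5.1 and SAP Section 3.1 say the same.

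**The concern.** Three statements of time on open-label treatment do not fit together: the Table 4 day count, the 12- and 36-week endpoint labels, and the SAP mapping. If treatment starts at or after a visit scheduled for Day 90, a visit fixed at Day 168 cannot give every subject 84 days on drug.

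Three things are at stake. First, the endpoint label would not describe the exposure behind it, and that exposure would differ between subjects without the tables showing it. Second, the week-24 result triggers withdrawal and so determines who can contribute week-48 data; that decision would be taken at unequal exposure. Third, the SAP measures compliance against planned dose. If planned dose assumes a Day 85 start, subjects who take every capsule but start later look under-dosed.

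**Working it through.** **Reproducing the SAP figures.** The SAP intervals are 4 days at 0.05 mg, 3 at 0.1 mg, 21 at 0.2 mg, then 56-day blocks at 0.2 mg.

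- Day 28: 4×0.05 + 3×0.1 + 21×0.2 = 4.7 mg over 28 doses.
- Day 84: 4.7 + 56×0.2 = 15.9 mg over 84 doses.
- Day 252: 15.9 + 3×56×0.2 = 49.5 mg over 252 doses.

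All three match. The mapping subtracts 84 throughout (112−28 = 168−84 = 336−252 = 84), so treatment day 1 must be study Day 85. That is the earliest day of the visit 12 window.

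**Permitted start days.** Titration cannot precede visit 12, so the start is Day 85 or later. With the last stage 1 dose on Day 84, a gap under 7 days requires start − 84 < 7, so Day 90 at the latest. On-schedule starts are therefore Days 85 to 90.

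**Doses by each visit.** Doses = visit day − start day + 1. The visit-day dose is counted because Table 4 requires dosing at the site on visit days.

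| Case | Start | Visit | Doses | Weeks (doses ÷ 7) |
|---|---|---|---|---|
| Week 24, earliest on-schedule start | 85 | 168 | 84 | 12.0 |
| Week 24, Day 90 start | 90 | 168 | 79 | 11.3 |
| Week 24, lowest permitted | 95 | 163 | 69 | 9.9 |
| Week 24, highest permitted | 85 | 173 | 89 | 12.7 |
| Week 48, Day 90 start | 90 | 336 | 247 | 35.3 |
| Week 16, Day 90 start | 90 | 112 | 23 | 3.3 |

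The 69-dose case is allowed: the week-12 visit is Day 84 ±5, so a last stage 1 dose on Day 89 and a first open-label dose on Day 95 leave a gap of 6 days.

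**Effect on compliance.** SAP Section 13 uses relative dose intensity, which is dose intensity divided by planned dose intensity. Both have the same duration as denominator, so the measure reduces to actual ÷ planned cumulative dose. For a fully adherent subject, actual dose = 0.5 + 0.2 × (doses − 7) mg. With a Day 90 start and the table applied by visit:

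- Treatment ending at Day 112: 0.5 + 0.2×16 = 3.7 mg; 3.7/4.7 = 79%, in the <80% category.
- Day 168: 0.5 + 0.2×72 = 14.9 mg; 14.9/15.9 = 94%.
- Day 336: 0.5 + 0.2×240 = 48.5 mg; 48.5/49.5 = 98%.

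At the lowest week-24 exposure (69 doses) the result is 0.5 + 0.2×62 = 12.9 mg; 12.9/15.9 = 81%.

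**Treatment length.** Weeks 13 to 48 are 48 − 13 + 1 = 36 weeks. One week of titration followed by 36 weeks at 0.2 mg is 37.

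**The case against.** **Day 90 is the screening day, not a stated treatment start.** The protocol text puts the one-week titration in week 13. Counted in sevens from Day 1, week 13 is Days 85 to 91, and a full week inside it starts on Day 85, so the SAP mapping has support in the text. This stands, and it is why 79 doses should be read as the lower end of an on-schedule range of 79 to 84. It does not remove the contradiction, because Table 4 centres visit 12 on Day 90. A subject starting then reaches titration Day 5 on Day 94, outside week 13.

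**The shortfall is within tolerance.** Five days is no more than the ±5 window the protocol accepts for the stage 1 week-12 visit, and 69 doses needs a late last stage 1 dose, a late start and an early week-24 visit together. Both points are fair and limit the size. But a visit window spreads exposure around the intended day, whereas here the two documents disagree on which day is intended.

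**The SAP may not apply its table rigidly.** Section 12 describes planned dose as what the subject should take, and Section 6 starts the sub-study 2 analysis period at the first open-label dose. The SAP does not say which reading governs, so the compliance figures are conditional on use by visit.

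**The 37-week reading may be loose wording.** The duration statements and Table 4 point to 36 weeks in total. That may be so, but the other wording appears in both documents and should be settled.

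**Stronger readings the documents do not support.** A reader might infer that low computed compliance removes sub-study 2 subjects from the per-protocol set. SAP Section 5.2 lists the 80% criterion only for sub-study 1. If that list were borrowed, a subject stopping at Day 112 would already be excluded for having no week-48 score. A reader might also infer that late starters are more often judged non-responders and withdrawn. That direction is conceivable, but the documents give no time course of response from which to size or establish it.

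**Conclusion.** The inconsistency is real and modest. For subjects whose last stage 1 dose is on Day 84 and whose visit is on Day 168, the week-24 endpoint and withdrawal decision fall after 79 to 84 doses, and only a Day 85 start gives 84. Across all permitted windows the range is 69 to 89. For a Day 90 start, week 48 falls 5 doses short of 252.

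It would be wrong to conclude that every subject is assessed early, since the windows also allow 84 to 89 doses. The effect is confined to exploratory endpoints, which SAP Section 14.4.2 reports descriptively for a single arm, and to the exposure and compliance summaries. The primary analysis is untouched, and no per-protocol effect in sub-study 2 is established.

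The dose counts assume daily dosing without missed days, counting the visit-day dose. The compliance percentages also assume that the SAP table is applied by visit.

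**What to change.** 1. In SAP Section 12, compute planned cumulative dose and dose intensity for sub-study 2 from each subject's actual first open-label dose date, and carry this into compliance in Section 13. A fully adherent Day 90 starter at Day 168 then scores 14.9/14.9 = 100%.
2. Report the distribution of actual days on open-label treatment at the week-24 and week-48 assessments, and label those endpoints by study week.
3. The sponsor must reconcile the Table 4 visit days, the endpoint labels, the SAP mapping and the two statements of treatment length. Because the week-24 visit carries a treatment-stopping decision, this review does not say which schedule is right.

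Items 1 and 2 cost SAP wording and some programming. They need no added visit or procedure, and they rest on the first open-label dose date, which SAP Sections 6 and 6.2 already use for the analysis period and baseline. They can be done even if all visits are complete. Item 3 is clarification of text.

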 - a. Immunosuppressants (such as cyclosporine, tacrolimus, sirolimus or mycophenolate mofetil), thalidomide or traditional Chinese medicine;
 - b. Approved non-biologic agents or traditional Chinese medicine treatment.
- 12. Patients who plan to concurrently use an immunosuppressant (such as azathioprine,

- 6-mercaptopurine or methotrexate) after randomization. Patients treated with azathioprine, 6-mercaptopurine or methotrexate at screening are required to discontinue it prior to the first dose of the study drug.
- 13. The subject has received any investigational biologic or non-biologic agent, or approved biologic agent or biosimilars within 60 days or 5 half-lives prior to screening (whichever is longer).
- 14. The subject has used topical (rectal) treatment with aminosalicylic acid, corticosteroid or traditional Chinese medicine enemas/suppositories or for UC treatment within 2 weeks of the administration of the first dose of study drug.

Exclusion criteria for general conditions:

- 15. The subject has any unstable or uncontrolled cardiovascular, pulmonary, hepatic, renal, gastrointestinal, genitourinary, hematological, coagulation, immunological, endocrine/metabolic, or other medical disorders that, in the opinion of the investigator, would confound the study results or compromise subject safety.
- 16. History of uveitis or macular oedema.
- 17. Clinically relevant cardiovascular conditions, including history or presence of any one of below:
 - a. Ischemic heart disease or myocardial infarction; Unstable angina; History of angina pectoris caused by coronary artery spasm, or raynaud's phenomenon (Raynauds);
 - b. Congestive heart failure (NYHA class III-IV), cardiac arrest;
 - c. Stroke, transient ischemic attack;
 - d. History of recurrent syncope or positive result of vasovagal syncope tilt test;
 - e. Symptomatic bradycardia, sick sinus syndrome, sinoatrial block, second degree atrioventricular block (e.g., Mobitz type 2 atrioventricular block) or third degree atrioventricular block;
 - f. Congenital long QT syndrome (LQTS), or prolonged QT interval corrected using Fridericia's formula (QTcF) in screening ECG (QTcF > 450 ms in men, QTcF > 470 ms in women);
 - g. Subjects at increased risk for QT prolongation due to hypokalemia or hypomagnesemia; or subjects who are currently taking medications to prolong QT interval (e.g., citalopram, chlorpromazine, haloperidol, methadone, and erythromycin) which result in risk for torsades de pointes;

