- 15. Blood chemistry tests on Day 15 (visit 6), 42 (visit 8) and 70 (visit 10) only include liver function tests.
- 16. At screening, serological tests are performed for all subjects to determine the subjects' immune status against the viruses: HIV antibody, HBsAg, HBsAb and HBcAb and anti-HCV.

 *Subjects with positive HBsAg will be excluded. HBV-DNA test should be carried out at screening if the subject is negative for HBsAg, negative or positive for HBsAb, and positive for HBcAb. The subject should be excluded from the study if HBV-DNA test result is positive, or he/her can be enrolled in the study in case of negative result of HBV-DNA test.

 **An HCV viral load test should be carried out if HCV antibody is positive in the subject. The subject should be excluded from the study in case of positive HCV viral load test result. If the HCV viral load test result is negative, the subject can be enrolled in the study.
- 17. If urinalysis show occult blood or abnormal urine protein in subjects' urine samples, a microscopy examination needs to be performed. A microscopy examination mainly focuses on the presence of white blood cells and red blood cells. All other parameters will be tested with test strips.
- 18. Fecal culture/microscopy (involving fecal culture, C. difficile, parasite ovas and parasites) is required to be performed at screening. During the screening period and at any time point during the study, if the subject has symptoms including aggravation of the disease condition or recurrence of previous disease activity, stool samples can be collected for fecal culture/microscopy and C. difficile analysis.
- 19. Within 14 days prior to randomization at screening, colonoscopy will be performed to obtain a Mayo endoscopic subscore and a complete Mayo score and then determine subject

Confidential

- eligibility. Colonoscopy will also be performed at week 12 (or early termination from the study visit).
- 20. On the days of visits during the study treatment period, the investigational product will be taken at the study sites and the time of administration will be recorded according to the study flow chart.

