7.3.11. Safety laboratory parameters

In the study, all samples except the PK blood sample will be analyzed in the central laboratory (Q Squared Solutions).

It is required to collect blood samples according to the Table 10 below. Details involving sample collection, transportation, results reporting, as well as laboratory reference ranges and abnormalities warning will be specified in the laboratory manual and provided to each study site prior to the initiation of the study.

This protocol clearly specifies the time points for collecting blood, urine and fecal samples (Table 2, Table 3, Table 4). To evaluate safety, the investigator can decide to conduct unscheduled laboratory tests at any time during the study.

Table 10. Safety Laboratory Parameters

Laboratory test item	Parameter
Hematology	Red blood cell (RBC) count, HGB, hematocrit (HCT), white blood cell count, blood platelet count, leukocyte differential count (lymphocyte count, neutrophil count, monocyte count, eosinophil count, basophil count)
Blood chemistry (fasting)	
Liver function test	Total bilirubin, conjugated bilirubin, ALT, AST, γ-GT, alkaline phosphatase, albumin, total protein, lactate dehydrogenase
Kidney function test	Urea, creatinine, uric acid, Na, K, Cl, Ca, P, amylase ¹
Blood glucose examination	Fasting blood glucose (FBG)
Fasting blood fat ²	Total cholesterol, low-density lipoprotein cholesterol, high-density lipoprotein cholesterol and triglycerides
Coagulation	Prothrombin time, activated partial thromboplastin time, and international normalized ratio
Urinalysis/microscopy ³	Specific gravity, pH, nitrite, protein, glucose, ketone bodies, urobilinogen, bilirubin, occult blood, esterase leukocyte/erythrocyte, and white blood cells
Fecal culture/microscopy 4	Fecal culture, C. difficile, parasite ovas and parasites, and fecal calprotectin
Others	
Virological and	HIV antibody, HBsAg, HBsAb, HBcAb and HCVAb
serological tests	Syphilis antibody
	HBV-DNA, HCV viral loads
Detection of immunoglobulin	Immunoglobulin A, G, M

Detection of C-reactive protein	C-reactive protein
Pregnancy test ⁵	Blood β-human chorionic gonadotropin and urine pregnancy test
Quantiferon or Quantiferon Plus test ⁶	ТВ

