10 DATA QUALITY ASSURANCE

The investigator is responsible for verifying that data entries are accurate and correct by physically or electronically signing the CRF. The investigator must maintain accurate documentation (source data) that supports the information entered in the CRF. Sponsor has the obligation of ethical, legal and scientific to carry out this study in accordance with the established clinical trial protocol, GCP and ICH-GCP guidelines. In order to fulfill these obligations and achieve study progress, in addition to ensuring telephone and written communication, sponsor's monitor or representative will visit the study site throughout the study. Sponsor's monitor or representative will conduct site monitoring visit, making calls, and do regular eCRF review, to evaluate subject enrollment, study protocol compliance, and integrity and accuracy of data entered into EDC system, and conduct source data verification and AE checking according to the original documents. Investigator must provide the monitor with all resources and study documents.

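### Exclusion 17g names hypokalemia and hypomagnesemia, but the screening chemistry measures potassium and not magnesium, so unrecognised low magnesium is found only by an optional unscheduled test.

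*Protocol*

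**What the plan says.** Criterion 17g appears in the Protocol synopsis and again in Section 5.4.1. Its first part excludes "Subjects at increased risk for QT prolongation due to hypokalemia or hypomagnesemia". It gives no numeric limit and names no test for either electrolyte. The opening line of exclusion 17 covers current conditions as well as past ones. The eligibility rule is strict: a subject may enter "only if all of the inclusion criteria apply and none of the exclusion criteria apply".

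The stage 1 flow chart (Protocol Table 2) schedules blood chemistry at screening and at baseline. Note 15 to that table reduces the panel at three later visits only: "Blood chemistry tests on Day 15 (visit 6), 42 (visit 8) and 70 (visit 10) only include liver function tests". Screening therefore uses the full panel. In Protocol Table 10 (Section 7.3.11) the kidney and electrolyte line of that panel reads "Urea, creatinine, uric acid, Na, K, Cl, Ca, P, amylase". SAP 15.3 gives the same list.

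Section 7.3.11 also allows further tests: "the investigator can decide to conduct unscheduled laboratory tests at any time during the study". It leaves operational detail to a separate document: "laboratory reference ranges and abnormalities warning will be specified in the laboratory manual".

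**The concern.** A criterion that binds every subject names two electrolytes, and the plan collects the value for only one of them. If a site follows the schedule exactly, it will have a potassium result for each screened subject and no magnesium result for any. Low magnesium already in the medical record can still be acted on. Low magnesium that nobody has noticed cannot, unless someone decides to look.

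Two things are at stake, both modest. One is patient safety: a subject whom the sponsor meant to keep out on QT grounds could receive a first dose. The other is even application of the criterion, since some sites may order magnesium and others may not. Data monitoring does not close the gap. Section 10 has monitors "conduct source data verification and AE checking according to the original documents", but that step cannot check a result that was never obtained.

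**Working it through.** The plan gives no figure to reproduce, and no power or error-rate calculation applies. The check is a comparison of the criterion with the scheduled tests.

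1. **Electrolytes named in 17g:** potassium and magnesium, so 2.
2. **Chemistry panel at screening (Table 10):** 9 liver analytes + 9 kidney and electrolyte analytes + 1 fasting glucose = 19. Adding the 4 fasting lipids, which Table 2 also schedules at screening, gives 19 + 4 = 23.
3. **Electrolytes in that panel:** Na, K, Cl, Ca and P, so 5. Potassium is present. Magnesium is absent from the 19 and from the 23.
4. **Coverage of 17g:** 1 of 2 named electrolytes has a scheduled test.
5. **Other places a magnesium result could come from:**
   - Exclusion 23 (screening laboratory abnormalities) sets limits for blood counts and creatinine, and exclusion 24 for liver tests. Neither mentions potassium or magnesium.
   - SAP 15.3 adds no magnesium.
   - The laboratory manual is not among the documents. Section 7.3.11 gives it collection, transport, reporting, reference ranges and alerts, and leaves the list of parameters to Table 10.
   - The unscheduled-test provision is the one remaining route, and it is optional.
6. **QT cover before the first dose (Table 2 with notes 5 and 6):** a screening ECG with the 17f limits (QTcF above 450 ms in men or 470 ms in women excludes), a day 0 ECG, and a day 1 pre-dose ECG. That is 1 + 1 + 1 = 3 ECG occasions, plus a day 0 Holter.
7. **QT cover in stage 1 titration:** 3 ECG time points (pre-dose, 4 h, 6 h) × 4 days (1, 2, 5, 8) = 12, the first of which is the day 1 pre-dose ECG already counted in step 6. Holter recordings on days 0, 1, 5 and 8 make 4.

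Steps 1 to 5 establish the gap. Steps 6 and 7 show why its practical consequence is small: those checks would show a prolonged QT interval, though none of them measures magnesium.

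**The case against.** The strongest reply is that 17g is a clinical-risk criterion and not a laboratory one. Where the protocol wants laboratory screening it says so, in exclusions 23 and 24, with analytes, limits and repeat rules. Other items under 17 can be applied from history: 17d refers to a positive tilt test, and no tilt test is scheduled. On this view an investigator applies 17g from what is known about the patient.

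Much of that stands. A reader might infer that 17g calls for a fixed cut-off, such as the laboratory's lower limit of normal. The documents do not support this. The criterion concerns increased QT risk, so a bare cut-off would exclude a marginally low value with a normal QTcF, and potassium in the same sentence has no limit either. What does not fall is the narrower point. The opening line of 17 includes present conditions, and an unrecognised low magnesium can be shown only by measuring it. The investigator's judgement needs a value to work on.

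The second reply is that QT risk is already controlled. Besides the ECG and Holter checks above:

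- 17k excludes a clinically significant screening ECG abnormality.
- Exclusion 15 removes unstable disorders that, "in the opinion of the investigator, would confound the study results or compromise subject safety".
- Section 6.6.2 bans QT-prolonging drugs.
- Sections 6.2.1 and 7.5 require further monitoring if QTc lengthens.
- Section 3.3.1 reports no QT or QTcF effect in dogs at 50 mg/kg and calls the drug's human QT potential very low.

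This is right, and it limits the point to a small improvement. A reader might infer that subjects with low magnesium would be dosed without QT protection; these provisions show otherwise.

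A reader might also extend the argument to exclusion 18, which mentions an HbA1c figure with no scheduled HbA1c. That does not follow. Exclusion 18 rests on history and investigator judgement, fasting glucose is in Table 10, exclusion 15 covers uncontrolled metabolic disorders, and no harm can be shown.

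**Conclusion.** The point holds as a minor, inexpensive improvement. It is certain that magnesium is absent from the scheduled panel in both documents, and that 17g names it. It follows that hypomagnesemia not already known is found only through an optional test.

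The size is 1 of 2 named electrolytes without a scheduled measurement. How many subjects this would affect cannot be derived, because the documents give no prevalence of low magnesium in this population. The residual risk is judged small because QT is checked repeatedly before and after the first dose. There is no effect on the primary endpoint, the significance level, the power or the randomised comparison.

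The conclusion assumes that Table 10 is the complete parameter list, as Section 7.3.11 presents it. If the laboratory manual already adds magnesium at screening, the remedy is only to bring Table 10 into line.

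**What to change.** Add serum magnesium to the Table 10 blood chemistry, marked for screening only and taken from the existing draw. Leave the wording of 17g as it is: the investigator judges a low potassium or magnesium result for QT risk. Allow a repeat test within the screening period, in line with the retest provisions in exclusions 23 and 24. Make the matching change in the SAP 15.3 table and the laboratory manual. No numeric cut-off is needed.

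The cost is one routine assay per screened subject, a manual update, and possibly a few more screen failures. No visit, procedure or staff is added.
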